## 7.0 MEASUREMENT OF EFFECT

### 7.1 Antitumor Effect- Solid Tumors

Response and progression will be evaluated in this study using the new international criteria proposed by the Response Evaluation Criteria in Solid Tumors (RECIST) Committee [Eur J Cancer 45(2): 228-47, 2009]. Changes in only the largest diameter (unidimensional measurement) of the tumor lesions are used in the RECIST v1.1.

#### 7.1.1 Definitions

Evaluable for toxicity. All patients will be evaluable for toxicity from the time of their first treatment with study drug.

Evaluable for objective response. Only those patients who have measurable disease present at baseline, have received at least 1 cycle(s) of therapy, and have had their disease re-evaluated will be considered evaluable for response. These patients will have their response classified according to the definitions stated below. (Note: Patients who exhibit objective disease progression prior to the end of cycle 1 will also be considered evaluable.)

#### 7.1.2 Disease Parameters

Measurable disease. Measurable lesions are defined as those that can be accurately measured in at least one dimension (longest diameter in the plane of measurement is to be recorded) with a minimum size of:

- 10mm by CT scan (irrespective of scanner type) for studies with a slice thickness of  $\leq$ 5mm or twice the slice thickness or MRI
- 10mm caliper measurement by clinical exam (lesions which cannot be accurately measured with calipers should be recorded as non-measurable)
- 20mm by chest X-ray (if clearly defined and surrounded by aerated lung)

All tumor measurements must be recorded in millimeters (or decimal fractions of centimeters).

**Malignant lymph nodes:** To be considered pathologically enlarged and measurable, a lymph node must be  $\geq$ 15mm in short axis when assessed by CT scan (CT scan slice thickness recommended to be no greater than 5 mm). At baseline and in follow-up, only the short axis will be measured and followed.

**Non-measurable disease.** All other lesions (or sites of disease), including small lesions (longest diameter  $<$ 20 mm with conventional techniques or  $<$ 10 mm using CT scan), are considered non-measurable disease. Bone lesions, leptomeningeal disease, ascites, pleural/pericardial effusions, lymphangitis cutis/pulmonis, inflammatory breast disease, abdominal masses (not followed by CT or MRI), and cystic lesions are all non-measurable.

**Target lesions.** All measurable lesions up to a maximum of 2 lesions per organ and 5 lesions in total should be identified as **target lesions** and recorded and measured at baseline. Target lesions should be selected on the basis of their size (lesions with the longest diameter), be representative of all involved organ, but in addition should be those that lend themselves to reproducible repeated measurements.

Lymph nodes merit special mention since they are normal anatomical structures which may be visible by imaging even if not involved by tumor. Pathological nodes which are defined as measurable and may be identified as target lesions must meet the criterion of a short axis of  $\geq$ 15mm by CT scan. Only the short axis of these nodes will contribute to the baseline sum. The short axis of the node is the diameter normally used by radiologists to judge if a node is involved by solid tumor. Nodal size is normally reported as two dimensions in the plane in which the image is obtained (for CT scan this is almost always the axial plane; for MRI the plane of acquisition may be axial, sagittal or coronal). The smaller of these measures is the short axis. For example, an abdominal node which is reported as being 20mm x 30mm has a short axis of 20mm and qualifies as a malignant, measurable node. In this example, 20mm should be recorded as the node measurement. All other pathological nodes (those with short axis  $\geq$ 10mm but  $<$ 15 mm) should be considered non-target lesions. Nodes that have a short axis  $<$ 10mm are considered nonpathological and should not be recorded or followed. A sum of the diameters (longest for non-nodal lesions, short axis for nodal lesions) for all target lesions will be calculated and reported as the baseline sum diameters. If lymph nodes are to be included in the sum, then as noted above, only the short axis is added into the sum. The baseline sum diameters will be used as reference to further characterize any objective tumor regression in the measurable dimension of the disease.

**Non-target lesions.** All other lesions (or sites of disease) including pathological lymph nodes should be identified as non-target lesions and should also be recorded at baseline. Measurements are not required, and these lesions should

be followed as 'present', 'absent', or in rare cases 'unequivocal progression' (more details to follow). In addition, it is possible to record multiple non-target lesions involving the same organ as a single item on the case record form (e.g. 'multiple enlarged pelvic lymph nodes' or 'multiple liver metastases').

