### 3.1 Inclusion Criteria

- 3.1.1 Advanced unresectable or metastatic sarcoma
  - Cohort 1: LMS/LPS
  - Cohort 2: Other histologies (excluding Gastrointestinal Stromal Tumors)
- 3.1.2 Must have received at least 1 prior standard systemic therapy regimen. For cohort 1 patients, this must have included a prior anthracycline.
- 3.1.3 Measurable disease by RECIST 1.1 criteria
- 3.1.4 Age  $\geq$  16 years
- 3.1.5 ECOG  $\leq$  1
- 3.1.6 Adequate hematologic, renal and hepatic function within 14 days prior to administration of study treatment as defined below:

Hemoglobin	$\geq 10$ g/dL with no blood transfusion within 28 days
Absolute neutrophil count	$\geq 1.5 \times 10^9$ /L
Platelets	$\geq 100 \times 10^9$ /L

Total Bilirubin	$\leq 1.5 \times$ institutional upper limit of normal (ULN).  NOTE: patients with elevated bilirubin secondary to Gilbert's disease are eligible to participate ( $<2.0 \times$ ULN should be used)
Aspartate aminotransferase (AST) & alanine aminotransferase (ALT)	$\leq 2.5 \times$ institutional ULN unless liver metastases are present in which case AST and ALT must be $\leq 5 \times$ ULN
Serum creatinine	Estimated or calculated creatinine clearance (Cockcroft-Gault formula) $\geq 51$ mL/min using the Cockcroft-Gault equation or based on a 24-hour urine test:  Estimated creatinine clearance = $(140 - \text{age} [\text{years}]) \times \text{weight} (\text{kg}) \times F^a$ serum creatinine (mg/dL) $\times 72$ a where F=0.85 for females and F=1 for males.

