### **11.0 STATISTICAL CONSIDERATIONS**

#### **11.1 Study Design/Study Endpoints**

This is a prospective, single-arm, multi-site study evaluating combination trabectedin and olaparib. Eligible patients will be assigned to one of two cohorts. Cohort 1 consists of patients with leiomyosarcoma or liposarcoma. Cohort 2 consists of patients with other bone or soft tissue sarcoma histologies. An independent Simon-minimax two-stage design will be used in each cohort.

The primary objective is to estimate the overall response rate (CR+PR) with an endpoint of objective response as based on RECIST 1.1 criteria anytime within a minimum of 18 months after start of treatment but no more than 2 years from registration. Secondary endpoints include PFS, OS and occurrence of adverse events. Exploratory endpoints include the presence of DNA repair defects by NGS and/or IHC and cardiovascular biomarkers.

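### Section 7.1.2 calls bone lesions non-measurable without exception while cohort 2 enrols bone sarcomas, so it is unclear whether a bone tumour's soft-tissue component counts towards response

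*Combined protocol and SAP*

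**What the plan says.** Section 7.1.2 starts from a general rule: "Measurable lesions are defined as those that can be accurately measured in at least one dimension". The minimum is 10 mm on CT with slices of 5 mm or less (otherwise twice the slice thickness), or on MRI.

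The paragraph on non-measurable disease then names sites. It begins "Bone lesions, leptomeningeal disease, ascites, pleural/pericardial effusions, lymphangitis cutis/pulmonis" and ends "abdominal masses (not followed by CT or MRI), and cystic lesions are all non-measurable". The only qualifier in that list belongs to abdominal masses. Bone has none, and a soft-tissue component is not mentioned anywhere in the document.

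The rest of the scoring chain is:

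- **Population.** Section 11.1: "Cohort 2 consists of patients with other bone or soft tissue sarcoma histologies".
- **Entry.** Criterion 3.1.3 asks for "Measurable disease by RECIST 1.1 criteria".
- **Targets.** Section 7.1.2: "All measurable lesions up to a maximum of 2 lesions per organ and 5 lesions in total should be identified as" targets. On choosing among them: "Target lesions should be selected on the basis of their size (lesions with the longest diameter), be representative of all involved organ".
- **Other lesions.** Section 7.1.2 makes everything else non-target. These lesions need no measurement and are tracked by category only.
- **PR.** Section 7.1.4.1 requires a fall of at least 30% from baseline in the target sum, with no new lesion. The table in 7.1.4.3 scores target PR with non-target disease short of progression, and no new lesion, as an overall PR.
- **Authority.** Section 7.1.1 has evaluable patients classified by the definitions that follow it.

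**The concern.** In a bone sarcoma the dominant tumour can be a bone lesion with a large soft-tissue mass. The site list, taken at its word, puts that mass among the unmeasured non-target lesions. Response then rests on whatever else is measurable, perhaps one small lung nodule. The size rule in the same section would count the mass. The instruction to choose targets by size and to represent every involved organ also cannot be met for bone if bone can never supply a target.

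Objective response is the primary endpoint, and cohort 2 is decided on very few events. A rule that can create a response, hide one, or let readers at two centres disagree on the same images bears directly on the stop/continue and promising/not-promising decisions.

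**Working it through.** **1. The plan's own figure.** Cohort 2 (section 11.2) enrols 13 patients, stops at 0 responses, otherwise adds 14, and declares success at 4 or more of 27. The null rate is 5% and the target 20%, with type 1 error 5% and power 80%. With X1 the stage 1 responses and X2 ~ Bin(14, p):

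P(success) = Σ over x = 1, 2, 3 of P(X1 = x) × P(X2 ≥ 4 − x), plus P(X1 ≥ 4).

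- At p = 0.05: 0.3512×0.0301 + 0.1109×0.1530 + 0.0214×0.5123 + 0.0031 = 0.0106 + 0.0170 + 0.0110 + 0.0031 = **0.0416**.
- At p = 0.20: 0.1787×0.5519 + 0.2680×0.8021 + 0.2457×0.9560 + 0.2527 = 0.0986 + 0.2150 + 0.2349 + 0.2527 = **0.8011**.

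The stated design is reproduced.

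**2. One scan under the two readings.** The lesion sizes are assumed: a bone-based mass measuring 90 mm and one 14 mm lung nodule. The 90 mm is taken to be soft tissue; if part of it is bone, only the soft-tissue dimension would enter the sum.

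| Change | Mass excluded | Mass counted |
|---|---|---|
| Nodule 14→9 mm, mass unchanged | (14−9)/14 = 36% fall: PR | (104−99)/104 = 5% fall: SD |
| Mass 90→55 mm, nodule unchanged | 0%: SD | (104−69)/104 = 34% fall: PR |

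**3. How far this depends on the 90 mm.** Let s be the soft-tissue dimension at baseline.

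- First row, component unchanged: the fall is 5/(14 + s). It drops below 30% once s exceeds 5/0.30 − 14 = 2.7 mm. Even a component at the 10 mm minimum gives 5/24 = 21%, so any qualifying component turns this PR into SD.
- Second row, component shrinking in the same proportion (35/90 = 38.9%): a PR needs 0.389s ≥ 0.30(14 + s), so s must be at least 0.30×14/(0.3889 − 0.30) = 47 mm. The missed-response case needs a substantial soft-tissue component.

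**4. What one patient can do.** A change from 0 to 1 response in the first 13 opens stage 2. A change from 3 to 4 in 27 turns the conclusion to promising. The reverse changes close stage 2 or turn a promising result into a failure.

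**5. Scenarios for the apparent response rate.** The formula in step 1 with a shifted rate gives:

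| Apparent rate | P(declare success) |
|---|---|
| 5% (null as planned) | 4.2% |
| 6% (one point of over-calling) | 7.2% |
| 20% (target as planned) | 80.1% |
| 19% (one point of missed response) | 76.5% |

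The one-point shifts are chosen for illustration. Nothing in the documents fixes their size or direction.

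**The case against.** The strongest reply is that this is a wording gap in a local summary. The text never says that an extraosseous mass is part of the bone lesion. Non-measurable disease is introduced as what remains after the size rule, and a discrete mass of 10 mm or more satisfies that rule. RECIST 1.1 is named throughout as the governing standard. Unequivocal non-target progression or a new lesion still gives progressive disease, and with several targets a single small nodule would not dominate the sum.

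Much of this stands, and it rules out three stronger readings that a reader might infer:

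- *The mass is certainly left out of the sum.* Only the literal reading of the list says so; the size rule points the other way.
- *A patient whose only disease is the mass cannot enrol.* Criterion 3.1.3 refers to RECIST 1.1 and does not cite 7.1.2. Such a patient may be judged ineligible if 3.1.3 is applied through 7.1.2, but the documents do not settle that.
- *The type 1 error of cohort 2 is really 7.2%.* That figure follows from an assumed one-point rise. The documents give no share of bone sarcomas, no lesion counts and no target sizes, and missed responses would pull the rate the other way.

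The reply does not remove the problem. Two tenable readings of one section are what let the same scan be scored PR by one reader and SD by another. Section 7.1.1 makes these definitions the operative ones, so a general reference to RECIST 1.1 does not tell a reader which to follow. The progression safeguard does not catch a mass that is unchanged or grows modestly.

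**Conclusion.** The concern holds as an unresolved conflict within section 7.1.2 that reaches the primary endpoint. The blanket listing of bone lesions disagrees with the size rule and with the target-selection rule beside it, in a trial that enrols bone sarcomas by design. Depending on the reading, a response can be created, hidden or scored differently by two readers, and one such patient is enough to change either decision in cohort 2.

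The net effect on error rates is unknown in size and sign, and the figures in step 5 are scenarios only. The lesion examples rest on assumed sizes and apply where the measured dimension is the soft-tissue component. The planned sample size and cut-offs are correct as computed and need no change. The point should be corrected, since the remedy is small and the endpoint is decided on single patients.

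**What to change.** In the non-measurable list of section 7.1.2, replace the entry for bone lesions with: *bone lesions without a soft-tissue component that meets the size rule above*. Add a sentence stating that a soft-tissue component of a bone lesion that meets the existing CT/MRI size rule is measurable and may be a target lesion, while the osseous part stays non-measurable. This also removes the doubt about eligibility when 3.1.3 is read through 7.1.2.

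The cost is a short text change. No scans are added, because footnote c of the Time and Events Table already requires CT and/or MRI of areas with disease. The downside is that the soft-tissue edge of a bone tumour is somewhat harder to measure; the existing preference in 7.1.2 for targets that can be measured reproducibly partly covers this.

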#### 7.1.3 Guidelines for Evaluation of Measurable Disease

All measurements should be recorded in metric notation, using calipers if clinically assessed. All baseline evaluations should be performed as close as possible to the treatment start and never more than 4 weeks before the beginning of the treatment.

The same method of assessment and the same technique should be used to characterize each identified and reported lesion at baseline and during follow-up. Imaging based evaluation should always be done rather than clinical examination unless the lesion(s) being followed cannot be imaged but are assessable by clinical exam.

**Clinical lesions:** Clinical lesions will only be considered measurable when they are superficial and >10mm diameter as assessed using calipers (e.g. skin nodules). For the case of skin lesions, documentation by color photography including a ruler to estimate the size of the lesion is suggested. As noted above, when lesions can be evaluated by both clinical exam and imaging, imaging evaluation should be undertaken since it is more objective and may also be reviewed at the end of the study.

**Chest X-ray:** Chest CT is preferred over chest X-ray, since CT is more sensitive than X-ray, particularly in identifying new lesions. However, lesions on chest X-ray may be considered measurable if they are clearly defined and surrounded by aerated lung.

**CT, MRI:** CT is the best currently available and reproducible method to measure lesions selected for response assessment. This guideline has defined measurability of lesions on CT scan based on the assumption that CT slice thickness is 5mm or less. When CT scans have slice thickness greater than 5 mm, the minimum size for a measurable lesion should be twice the slice thickness. MRI is also acceptable in certain situations (e.g. for body scans).

**Ultrasound:** Ultrasound is not useful in assessment of lesion size and should not be used as a method of measurement. If new lesions are identified by ultrasound in the course of the study, confirmation by CT or MRI is advised. If there is concern about radiation exposure at CT, MRI may be used instead of CT in selected instances.

#### 7.1.4 Response Criteria

##### 7.1.4.1 Evaluation of Target Lesions

**Complete Response (CR):** Disappearance of all target lesions, determined by two separate observations conducted not less than 4 weeks apart. There can be no appearance of new lesions.

**Partial Response (PR):** At least a 30% decrease in the sum of the longest diameter (LD) of target lesions, taking as reference the baseline sum LD. There can be no appearance of new lesions.

Progressive Disease (PD): At least a 20% increase in the sum of the LD of target lesions (with a minimum absolute increase of 5 mm), taking as reference the smallest sum LD recorded since the treatment started, or the appearance of one or more new lesions.

Stable Disease (SD): Neither sufficient shrinkage to qualify for PR nor sufficient increase to qualify for PD, taking as reference the smallest sum LD since the treatment started.

#### 7.1.4.2 Evaluation of Non-Target Lesions

Complete Response (CR): Disappearance of all non-target lesions and normalization of tumor marker level.

Incomplete Response/Stable Disease (SD): Persistence of one or more non-target lesion(s) and/or maintenance of tumor marker level above the normal limits.

Progressive Disease (PD): Appearance of one or more new lesions and/or unequivocal progression of existing non-target lesions.

#### 7.1.4.3 Evaluation of Best Overall Response

The best overall response is the best response recorded from the start of the treatment until disease progression/recurrence (taking as reference for progressive disease the smallest measurements recorded since the treatment started). The patient's best response assignment will depend on the achievement of both measurement and confirmation criteria.

Target Lesions	Non-Target Lesions	New Lesions	Overall Response	Best Response for this Category Also Requires:	
CR	CR	No	CR	>4 wks. Confirmation	
CR	Non-CR/SD	No	PR	>4 wks. Confirmation	
PR	Non-PD	No	PR		
SD	Non-PD	No	SD	documented at least once $\geq$ 4 wks. from baseline	
PD	Any	Yes or No	PD	no prior SD, PR or CR	
Any	PD*	Yes or No	PD		
Any	Any	Yes	PD		
* In exceptional circumstances, unequivocal progression in non-target lesions may be accepted as disease progression.					

Note: Patients with a global deterioration of health status requiring discontinuation of treatment without objective evidence of disease progression at that time should be reported as "symptomatic deterioration". Every effort should be made to document the objective progression even after discontinuation of treatment.
					

Note: If subjects respond to treatment and are able to have their disease resected, the patient's response will be assessed prior to the surgery.

#### 7.1.5 **Duration of Response**

Duration of overall response: The duration of overall response is measured from the time measurement criteria are met for CR or PR (whichever is first recorded) until the first date that recurrent or progressive disease is objectively documented (taking as reference for progressive disease the smallest measurements recorded since the treatment started). Patients without disease progression should be censored at the last time point for which their disease was known to not have progressed.

The duration of overall CR is measured from the time measurement criteria are first met for CR until the first date that recurrent disease is objectively documented.

Duration of stable disease: Stable disease is measured from the start of the treatment until the criteria for progression are met, taking as reference the smallest measurements recorded since the treatment started.

#### 7.1.6 **Progression-Free Survival**

Progression-free survival (PFS) is defined as the duration of time from start of treatment to time of progression.

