### 1.2 Study Agent(s) Background

#### Trabectedin

Trabectedin is a synthetic marine-derived drug that is known to have activity in advanced soft-tissue sarcoma (STS) and is currently approved for treatment in unresectable or metastatic leiomyosarcoma (LMS) and liposarcoma (LPS) previously treated with an anthracycline. A phase II study of trabectedin after standard chemotherapy as compared to best supportive care in various subtypes of STS showed a median progression free survival (PFS) of 5.6 months versus 0.9 months with a hazard ratio (HR) of 0.70 [1]. The most common adverse events were nausea, anorexia, neutropenia, and increased alanine aminotransferase. A subsequent phase III trial was conducted to evaluate the safety and efficacy of trabectedin versus dacarbazine in metastatic LMS and LPS. A total of 518 patients were enrolled and trabectedin-treated patients had a significantly improved PFS as compared to dacarbazine, 4.2 vs 1.5 months respectively with a HR of 0.55 [2]. Trabectedin has also been evaluated in the front-line setting in a phase IIb study comparing trabectedin to doxorubicin in patients with advanced or metastatic untreated STS. There was no significant improvement in PFS in the trabectedin arm as compared to doxorubicin, therefore doxorubicin remains standard of care as first-line therapy [3].

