### 2.4 Endpoints

The primary endpoint is objective response (CR + PR) as based on RECIST 1.1 criteria anytime within a minimum of 18 months after start of treatment but no more than 2 years from registration. Disease response will be assessed after 2 cycles ( $\pm$  7 days), then every 3 cycles thereafter.

Secondary endpoints include progression-free survival as time from start of treatment to progression or death, or censored at the date of last tumor assessment if no progression and alive; overall survival, as time from start of treatment to death, or censored at the date of last follow-up if alive and occurrence of adverse events as graded by CTCAE v5.0.

Exploratory endpoints include the presence of mutations in DNA repair genes identified by next generation sequencing, presence of DNA repair defects identified by IHC changes in novel cardiovascular biomarkers.

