
a. Olaparib is administered with continuous twice daily dosing
 
b. Vitals = temperature, pulse, respirations, blood pressure.
 
c. CT and/or MRI scans to cover bodily areas in which there is disease or suspected disease. Baseline scans to be obtained within 28 days of registration. Restaging scans will be repeated at C3D1 (<math>\pm 7</math> days) then every 3 cycles (<math>\pm 7</math> days) until disease progression. If clinical concerns for progression or significant delays in cycle length, imaging assessment may be obtained early at the discretion of the treating physician and continued at an interval of every 3 cycles at minimum. Scans should be obtained at the end of treatment visit if there is no prior radiographic confirmation of disease progression. The same method of assessment (i.e. CT, MRI) and the same technique should be used to characterize each identified and reported lesion at baseline and during follow-up. RECIST 1.1 guidelines will be used.
 
d. Hematology: CBC with differential to include WBC, hemoglobin, platelet count, absolute neutrophil count, absolute lymphocyte count and mean cell volume
 
e. Albumin, alkaline phosphatase, total bilirubin, bicarbonate, BUN, calcium, chloride, creatinine, glucose, potassium, total protein, SGOT (AST), SGPT (ALT), sodium
 
f. Activated partial thromboplastin time (APTT) and International normalized ratio (INR) will be performed at screening and if clinically indicated. For patients on warfarin it is recommended that INR monitored at least weekly for the first cycle and then on day 1 of each cycle thereafter, if stable. Each coagulation test result will be recorded in CRF.
 
g. Urinalysis to include measurement of hemoglobin/red blood cells/ or blood, protein or albumin, and glucose
 
h. Pregnancy tests on blood or urine samples will be performed for women of childbearing potential within 28 days prior to the start of study treatment, on Day 1 of the study prior to commencing treatment and at start of each cycle and at the 30 day follow up visit. Tests will be performed by the hospital's local laboratory. If results are positive the patient is ineligible/must be discontinued from study treatment immediately. Details of the pregnancy tests must be recorded in the patient's medical records.
							

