- i. Transthoracic echocardiogram (TTE) will be obtained at baseline to ensure adequate LVEF. Repeat TTE will be obtained every 3 cycles ( $\pm 1$  cycles) while on trabectedin or if clinical concern of decline in ejection fraction. MUGA can be performed if inadequate assessment by TTE per standard practice.
- j. Assessment of cardiovascular biomarkers including suPAR, BNP, high-sensitive troponin-I and high-sensitivity CRP will be obtained at baseline and after 2 doses of trabectedin on cycle 3 day 1.
- k. Results of NGS (if available) and archival tumor tissue to test for the presence of alterations in DNA repair pathways. Patients will not be asked to undergo an additional biopsy to obtain tumor sample. Full reports must be provided by the investigator for documentation on the Patient Safety database. These data are not required to be entered into CRF.
- l. Bone marrow or blood cytogenetic samples may be collected for patients with prolonged hematological toxicities at any timepoint as clinically indicated as defined in Section 5.2. Bone marrow analysis should include an aspirate for cellular morphology, cytogenetic analysis and flow cytometry, and a core biopsy for bone marrow cellularity. If it is not possible to conduct cytogenetic analysis or flow cytometry on the bone marrow aspirate, then attempts should be made to carry out the tests on a blood sample.
- m. Patients will be followed every 3 months via phone for documentation of progression and survival status for a minimum of 2 years from registration. If patient is unavailable, then survival status will be determined if possible, by public available information.
- n. Visits on day 1 of each cycle, lab measurements at days 1, 8 and 15 of each cycle, and the end of treatment visit, can be completed  $\pm 3$  days.

\* Screening labs to be obtained within 14 days of initiation of therapy. Baseline imaging to be obtained within 28 days of initiation of therapy.

\*\* Laboratory assessment will be done on day 8 for first 2 cycles to monitor for cytopenias.

Continued day 8 laboratory assessment beyond cycle 2 is at the discretion of the treating physician.

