### **11.3 Data Analyses Plans**

To address the primary objective, the overall response rate will be calculated as the proportion (and exact binomial 95% confidence interval) of patients with complete or partial response as defined by RECIST 1.1, within each cohort.

To address the secondary objectives:

- a. Progression free survival (PFS) will be calculated by the Kaplan-Meier method with errors according to Peto, within each cohort. Median and 6-month PFS will be estimated along with their 95% confidence intervals.
- b. Overall survival (OS) will be calculated by the Kaplan-Meier method with errors according to Peto, within each cohort. Median, 1- and 2-year OS will be estimated along with their 95% confidence intervals.
- c. The frequency and rates of adverse events occurring in at least 5% of participants and rates of grade 3-5 adverse events will be tabulated by system organ class and preferred term using Common Terminology Criteria of Adverse Events (CTCAE), within each cohort.

To address the exploratory objectives:

- a. The frequency and proportion of alterations in tumor sequencing will be summarized within each cohort.
- b. The frequency and proportion of alterations in DNA damage repair pathways will be summarized within each cohort.
- c. Changes in levels of novel cardiovascular biomarkers will be summarized and compared to clinical and echocardiographic cardiotoxicity.

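### PFS has two conflicting definitions: section 2.4 counts progression or death, section 7.1.6 counts progression only, and section 11.3 does not say which applies

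*Combined protocol and SAP*

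**What the plan says.** Section 2.4 (Endpoints) gives PFS as "time from start of treatment to progression or death, or censored at the date of last tumor assessment if no progression and alive". Section 7.1.6, the only section headed Progression-Free Survival, says "Progression-free survival (PFS) is defined as the duration of time from start of treatment to time of progression". Both are current text, and both start the clock at the start of treatment.

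Section 11.3 specifies Kaplan-Meier with Peto errors in each cohort and states that "Median and 6-month PFS will be estimated along with their 95% confidence intervals". It defines no event and refers to neither section. The objective in 2.2.1 ties PFS to RECIST 1.1 without mentioning death, and 11.1 only lists PFS as a secondary endpoint.

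Several provisions affect how often a patient could die without documented progression:

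- The table in section 6.2 shows tumor measurements at screening, during treatment and at the off-treatment visit. The follow-up column has none.
- Note c to that table adds that "Scans should be obtained at the end of treatment visit if there is no prior radiographic confirmation of disease progression".
- Note m says that "Patients will be followed every 3 months via phone for documentation of progression and survival status".
- Section 7.1.4.3 allows a patient to stop for symptomatic deterioration without objective progression, and adds that "Every effort should be made to document the objective progression even after discontinuation of treatment".

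**The concern.** The two definitions treat a patient who dies before progression is documented differently. Under 2.4 the death is a PFS event. Under 7.1.6 it is not, and because that section has no censoring rule, the analyst must invent one. What 7.1.6 describes is time to progression.

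The section just before it points the same way. For duration of response, 7.1.5 ends the interval at documented progression and says "Patients without disease progression should be censored at the last time point for which their disease was known to not have progressed", without separating patients who died from those still alive. Someone working from chapter 7 could handle PFS likewise.

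This is a single-arm trial. The synopsis names historical single-agent trabectedin as the reference, and section 1.2 cites a trabectedin arm with "significantly improved PFS as compared to dacarbazine, 4.2 vs 1.5 months respectively". With no concurrent control, a shift caused by the event definition is not cancelled by a comparator. If the definition is left open until the data are in hand, it could also be chosen after the results are seen.

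**Working it through.** **1. The definitions side by side**

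| | Section 2.4 | Section 7.1.6 | Section 11.3 |
|---|---|---|---|
| Origin | Start of treatment | Start of treatment | Not stated |
| Progression is an event | Yes | Yes | Not stated |
| Death is an event | Yes | Not mentioned | Not stated |
| Censoring | Last tumor assessment if alive and progression-free | None given | Not stated |

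No section states which definition takes precedence. The plan gives no PFS target, event count or power, so there is no stated figure to reproduce.

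**2. Direction**

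Suppose a death without progression is censored at the death date. The risk sets are then the same under both definitions, and the progression-only Kaplan-Meier curve simply omits the downward steps at those deaths. It can only equal or exceed the 2.4 curve. If the patient is instead censored at the last scan, the risk set shrinks earlier and the ordering is no longer guaranteed in every sample.

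**3. Size (illustration for cohort 1)**

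Inputs:

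- Composite median 4.2 months, the trabectedin figure cited in section 1.2.
- Share s of first events that are deaths without documented progression. The documents give no value. I assume 5%, 10%, 20% and 30%.
- Exponential times, with such deaths independent of progression.
- Maximum cohort size 26 (section 11.2).

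Formulas:

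- Total hazard: λ = ln 2 / 4.2 = 0.165 per month.
- Under 2.4: 6-month rate = exp(−6λ) = 0.371.
- Progression only, deaths censored at the death date: median = 4.2 / (1 − s); 6-month rate = exp(−6λ(1 − s)).

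| s | Median, months | 6-month rate |
|---|---|---|
| 0 (same as 2.4) | 4.20 | 0.371 |
| 5% | 4.42 | 0.390 |
| 10% | 4.67 | 0.410 |
| 20% | 5.25 | 0.453 |
| 30% | 6.00 | 0.500 |

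**4. Sensitivity to where the death is censored**

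This was simulated with 20,000 trials of 26 patients, scans at week 6 and then every 9 weeks (2 cycles, then every 3 cycles of 21 days), and no other censoring. Entries are the mean 6-month Kaplan-Meier estimate and, in the last column, how often it fell below the 2.4 estimate from the same data.

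| s | Censored at death | Censored at last scan | Last-scan estimate below 2.4 |
|---|---|---|---|
| 5% | 0.391 | 0.388 | 2.5% of trials |
| 10% | 0.410 | 0.404 | 2.1% |
| 20% | 0.453 | 0.442 | 0.7% |
| 30% | 0.500 | 0.483 | 0.2% |

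With censoring at the death date, the estimate was never below the 2.4 estimate, as step 2 requires.

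**5. Scale against sampling error**

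The approximate 95% half-width for a 6-month rate of 0.371 with 26 patients is 1.96 × √(0.371 × 0.629 / 26) = 0.186, about 19 percentage points.

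**The case against.** The best reply is that 2.4 would govern in practice. It is the endpoints section, and it gives origin, events and censoring. A Kaplan-Meier analysis cannot be run from 7.1.6 alone because that section has no censoring rule. Section 11.3 also leaves overall survival undefined, and 2.4 is the only place that defines it, so an analyst has to open 2.4 and will meet the PFS definition there. This is persuasive about what is likely. It does not remove the conflict: no precedence is stated, the PFS objective refers to RECIST 1.1, and the RECIST criteria are in chapter 7, where the only section bearing the endpoint's name omits death.

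Three further points stand in part:

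- **Duration of response.** It is not a stated objective, endpoint or planned analysis, and carrying its censoring rule over to PFS is conjecture. It is supporting context only. The conflict between 2.4 and 7.1.6 does not need it.
- **Scans after treatment.** Note c says restaging continues until progression, which could be read as extending beyond the end of treatment. But it counts scans in treatment cycles, and the follow-up column has no tumor measurement, so the on-treatment reading fits better. The end-of-treatment scan, the phone follow-up and the instruction to document progression all reduce the number of affected deaths.
- **The illustration.** The shares have no source in the documents. Good performance status and a life expectancy of at least 16 weeks at entry, with a first scan at about week 6, point to the lower end. The 20% and 30% rows show sensitivity and are not expectations. Independence is doubtful for deaths that follow clinical deterioration, the 4.2-month median comes from monotherapy, and nothing here is calibrated to cohort 2.

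**Conclusion.** The concern holds. Section 7.1.6 gives a definite rule that contradicts the endpoint definition in 2.4, and nothing in the plan resolves it. Followed as written, it would report time to progression as PFS.

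The likely effect is modest. At assumed shares of 5% to 10%, the 6-month rate rises by about 2 to 4 points and the median by 0.2 to 0.5 months. That is small beside a half-width of about 19 points, but it is one-sided: always upward or nil if deaths are censored at the death date, and nearly always upward in the simulation if they are censored at the last scan. Larger shares would give larger shifts, up to 13 points and 1.8 months at 30%, but the documents do not support any particular share.

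PFS has no test, target or decision rule in this trial. The response endpoint, the two-stage rules and the sample size do not depend on it. The contradiction itself is certain from the text. Whether 7.1.6 would actually be followed is not. It should be corrected before analysis.

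**What to change.** Replace the sentence in 7.1.6 with the 2.4 definition, spelled out: time from start of treatment to the first of RECIST 1.1 progression or death from any cause, censored at the last tumor assessment for patients alive without progression. The words *first of* and *from any cause* are not in 2.4 but only make its meaning explicit. In 11.3, state that PFS is analysed as defined in 2.4. If the progression-only quantity is also wanted, name it time to progression, give it its own censoring rule for deaths, and report it separately.

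The cost is one sentence and one cross-reference. No new data are needed, because survival status is already collected in follow-up. Reported PFS may be less favourable than a progression-only figure would have been. If 2.4 was always the intended definition, no result changes.
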